MR Content. The program provides video and audio instruction in a set of 11 evidence-based wellness activities in three thematic categories: *Connecting with Yourself*, *Connecting with Quiet*, and *Connecting with Your Partner*. All instruction is accessible via the program website (MissionReconnect.com) and mobile device apps. Video content totals 91 minutes and was produced by filming two days of workshops to teach the practices to Veteran/partner dyads. The *Program Overview* video (54 min.) introduces the MR instructional sequences accompanied by commentary by workshop participants. Detailed massage instruction is presented in the separate *Massage Instruction* video (34 min.) and *Massage Video Supplement* (3 min.) addressing use with home furniture. Users are encouraged to give and receive at least one massage per week. Audio content totals 67 minutes and was recorded in studio, with *nine instructional audios* ranging from one to 22 minutes. Users are encouraged to listen, learn the practices, and then use each technique with or without the guided instruction as they wish. Support materials. A *Massage Instruction Booklet* and illustrated *Massage Reminder Handout* are downloadable from the website. A *What if?* feature enables users to access advice on how to apply program techniques in challenging situations such as experiencing problems with sleep, focus and concentration. Users can submit questions and suggestions for future content through the *What if?* interface. *Optional Audios* give users choice of audio gender voice. A *Resources* section provides links to hotlines, Vet Centers and VA Facilities.

Users will be instructed to (1) try all the practices at least once during the first two weeks, and thereafter (2) do at least one exchange of massage per week with their partner, and (3) practice other methods of their choice at least 3 to 4 times per week. Dyads will be informed that greater use may result in greater benefit to reinforce practice.

Usual Care Waitlist Control Arm: For ethical reasons, this study will use a waitlist control

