To test **Aim 1 & Aim 2**, survey data will be collected using Qualtrics, a resource that has demonstrated capacity for remotely and securely collecting participant data in other studies conducted within the VA system. Qualtrics is a secure platform for the creation and distribution of online surveys and recording of response data, including quality control features such as range checks, skip patterns, and completeness of data entry. Qualtrics ensures protection and reliability of client data with high quality firewall systems, regular vulnerability scans, nightly complete backups, and annual complete

penetration tests. Qualtrics services will allow control of individual permissions for accounts and surveys. Qualtrics accounts are password protected, and all data are replicated in real-time. The participants will be assigned a unique PIN and will receive email messages with a link to prompt participant dyads to access the site and complete data collection. Upon access to Qualtrics, participants will be required to enter their PIN as the first entry into the system. Similarly, access to the online Mission Reconnect content will require entry of the same PIN. The PIN selected by each participant will be maintained in a cross-walk file with their randomly assigned study ID number. The Qualtrics measures will be compiled into a single survey format and collected at baseline, 1, 2, and 4 months. The rationale for this schedule is to formally assess initial, short-term, and sustained effects that may occur with the MR intervention. MR will utilize an outcome measure named *Self-Assessment of Change*^{62,63}. This tool was uniquely designed to assess a wide range of shifts in well-being across complementary and alternative medicine (CAM), therapeutic modalities and conditions. MR use and satisfaction, pain, tension and stress items will be conducted weekly for the first 8-weeks of data collection. This more frequent schedule of data collection will permit short-term dose-response analyses (i.e. dose of MR utilization) in relation to major symptoms of pain and PTSD. Measures and psychometric properties are illustrated in Table 1.

Table 1: Veteran and Partner Measures and Psychometric Properties

Construct	Measure	Description	Min.	Time point
Veteran Eligibility Variable				

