	Sleep Quality: Pittsburgh Sleep Quality Index ⁷¹	19 self-rated questions from which 7 component scores are calculated and summed into a global score to assess sleep quality in the past month.	4	
Veterans and Partner Independent Variable - Covariate				
MR Program Utilization (Treatment and Control group)	Utilization survey	Treatment group: weekly report 11-items will assess frequency of use and compliance of the MR mind/body & massage practices. Control group: weekly report 4-items with descriptive activities to obtain descriptive data on their utilization of any personal strategies to address stress coping, physical pain, partner relationship support, and sleep quality.	3	weeks 1-8; months 1, 2, 4
Veterans and Partner Dependent Variables				
Relationship Satisfaction	Revised Dyadic Adjustment Scale ⁷² - Adapted	14-item Likert-scaled instrument is reliable and valid and contains subscales for dyadic consensus, dyadic satisfaction, and dyadic cohesion.	3	Baseline, months 1, 2, 4

Compassion	Compassion for Self and Others Scales ^{73,74}	26- (CSS) and 21- item (COS) measures, five-point Likert-scaled measures self-compassion and compassion for others.	5	
Program Satisfaction (Treatment Only)	MR Program Satisfaction Items	11 ten-point Likert-type items assess satisfaction using MR components, whether they would recommend MR, and massage satisfaction.	1	Weeks 1-8; months 1, 2, 4

(2) Telephone interviews.

To address **Aim 3**, telephone interviews (~30 min) will be conducted with a sub-sample of 84 individuals. Only treatment group members will be recruited for this data collection. Prospective interviewees will be purposively selected (e.g., high or low MR utilization groups) to participate in telephone interviews to evaluate their experiences using the program. MR utilization will be calculated at the dyadic level. Both Veteran and partner members of dyads assigned to the treatment arm will be contacted for qualitative interviews, however interviews will be conducted with Veterans and their partners separately. We will explain the interview purpose and ask permission to audio-record and use the interview script to ensure that all topics are covered. An audio voice consent must be completed and voice recorded at the time of the telephone interview process. The participant will be informed they will be recorded and need to state on the recorded telephone interview when asked if they agree to participate prior to the start of the telephone interview.

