Hypotheses Aims 1 & 2. All outcome measures (*primary and secondary*) under Aim 1 will be collected at baseline, 1, 2, and 4 months and are continuous variables. Therefore, general linear mixed models will be used with main effects terms for GROUP (MR vs. waitlist) and TIME (4-time points) and a GROUP x TIME interaction term (for rate of change). The models will also include site as a random effect. To assess whether the rate of change is curvilinear (i.e., the rate of change differs between time points), a quadratic parameter will be tested. Different correlation structures and functional forms of the effects of the MR program will be assessed using the information criteria and a final parsimonious model will be determined for final statistical inference. Initial effects of the MR program (baseline to 1-month) will be evaluated by analysis of covariance (ANCOVA). For H1.1, the primary outcome measure for pain will be total score on the 19-item POQ. For H1.2., the primary outcome measure for PTSD will be total score on the 20-item PCL-5. Subgroup analyses will be explored using similar methods and examination of severity of baseline pain and PTSD scores. These analyses will provide insight into subgroups in whom the MR program may be particularly beneficial. In a similar realm, analyses will be stratified by baseline median level of relationship satisfaction, as derived from total score on the 14-item RDAS. This will permit assessment of the effect of the MR intervention on potential improvement in relationship satisfaction among a cohort of dyads with presumably troubled relationships at entry. Moreover, using the weekly reports (8 weeks) of MR use and satisfaction with the MR program, the MR sample will be split above versus below the median for these two measures, and compared separately against the waitlist control condition at 2-months. This approach approximates a “per protocol” analysis in terms of recommended use of the MR program. In addition, especially for Aim 2 outcomes, we seek to examine whether dyads appear to show mutual benefits from the MR program. Therefore, multilevel models will be fit using an over-time dyadic model⁷⁸ in which individuals are nested within dyads and time is crossed with dyads (i.e., both Veteran and partner are assessed at the 4 time points). This analysis accounts for the non-independence due to the correlation between dyad members’ general levels on outcomes averaged over time, as well as the time-specific correlation between their outcomes (e.g., similarity caused by time-specific events).

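### The planned comparison of above- and below-median halves of the MR arm with the waitlist is not randomised, and a median does not measure recommended use

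*Combined protocol and SAP*

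**What the plan says.** Under Data Analysis, Hypotheses Aims 1 & 2, the eight weekly reports supply two measures, MR use and MR satisfaction. On each of them "the MR sample will be split above versus below the median for these two measures, and compared separately against the waitlist control condition", with the outcome taken at 2 months. The plan says this comes close to a per-protocol "analysis in terms of recommended use of the MR program".

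Four other places bear on it:

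- **MR Content** defines what users are told to do. They are to try every practice in the first two weeks, then exchange massage at least weekly and "practice other methods of their choice at least 3 to 4 times per week".
- **Table 1** describes the treatment arm's use survey: "weekly report 11-items will assess frequency of use and compliance of the MR mind/body & massage practices". For the waitlist it has a different survey: "Control group: weekly report 4-items with descriptive activities to obtain descriptive data on their utilization of any personal strategies". Satisfaction is collected in the MR arm alone ("Program Satisfaction (Treatment Only").
- **Data Analysis**, opening paragraph, applies intention to treat to every analysis, whatever the compliance or dropout.
- **Updated Statistical Analysis Plan** lists use and satisfaction among the weekly data and points back to Table 1. It neither repeats nor withdraws the median split.

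**The concern.** Use and satisfaction are recorded after randomisation, and only the MR arm has them. Splitting that arm and setting each half against an undivided waitlist compares a selected group with an unselected one. Anything that makes some Veterans both use MR more and report different outcomes will then look like an effect of MR.

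The label adds to the problem. A reader who sees a per-protocol result will take the upper half to be those who followed the instruction, but a sample median puts half the arm there however much or little it practised. If the primary comparison (H1.1, total POQ score) came out weak or null, a significant upper-half contrast could be read as showing that MR works when used as recommended. The protocol says the weekly data "will permit short-term dose-response analyses (i.e. dose of MR utilization) in relation to major symptoms of pain and PTSD", so a reading by dose is at least within the plan's scope.

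**Working it through.** The plan gives no sample size, effect, test or error rate for this analysis, so there is no figure of its own to reproduce.

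**1. Is the contrast randomised?** A randomised comparison of high users needs the waitlist Veterans who would have been high users. Table 1 provides no variable to find them: the control survey covers personal coping strategies, and satisfaction is not asked. The same paragraph of Data Analysis also stratifies by relationship satisfaction, but at its baseline median, which both arms have. That split keeps the randomised comparison within each stratum. The use and satisfaction splits do not. They also group people by compliance, which the intention-to-treat sentence says no analysis will do.

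**2. Does the median stand for recommended use?** Let a be the share of the MR arm that meets the MR Content instruction. This share is assumed, because the documents do not give it.

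- At most a/0.5 of the upper half can meet the instruction. With a = 20%, that is 0.20/0.50 = 40%.
- At least (a − 0.5)/0.5 of the lower half must meet it. With a = 80%, that is 0.30/0.50 = 60%.

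The halves match the instruction only if about half the arm meets it and the use score ranks people in the same order. Satisfaction does not measure use. It is collected over the weeks leading up to the 2-month outcome, so it may follow from improvement rather than precede it.

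**3. How large could the distortion be? (illustration only)** Suppose use is a purely prognostic marker, correlated r with outcome, and MR has no effect. Outcomes are in SDs of the outcome as analysed; if baseline is adjusted for, r is the correlation that remains.

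- Mean of the upper half of a standard normal: √(2/π) = 0.798. The shift is therefore +0.798r in the upper half and −0.798r in the lower half.
- Standard error for n/2 against n: √(2/n + 1/n) = √(3/n).
- Chance of a falsely significant upper-half benefit at two-sided 0.05: about Φ(0.798r/√(3/n) − 1.96).

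The documents give both 200 dyads (Sample) and 600 dyads (Study Design and Overview), with about 33% attrition. These lead to 200 × 0.67/2 = 67 per arm (66 used, for equal halves) and 600 × 0.67/2 = 201 per arm (200 used). The second assumes that every site reaches its ceiling of 200 dyads.

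| r | shift (SD) | n = 66, SE 0.213 | n = 200, SE 0.122 |
|---|---|---|---|
| 0 | 0 | 2.5% | 2.5% |
| 0.1 | 0.08 | Φ(−1.59) = 6% | Φ(−1.31) = 10% |
| 0.2 | 0.16 | Φ(−1.21) = 11% | Φ(−0.66) = 25% |
| 0.3 | 0.24 | Φ(−0.84) = 20% | Φ(−0.01) = 50% |

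A simulation with pooled t tests and 80,000 replicates per cell agrees: 6, 11 and 20% at 66 per arm, and 9.5, 25.5 and 50% at 200. A negative r reverses the direction. At r = −0.2 the upper half shows false harm in 11% and 25% of runs.

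**The case against.** The plan is modest about this analysis. It claims only an approximation, and the neighbouring subgroup work is described as exploratory. The Updated SAP restates the models without the split, so it may no longer be intended. The value of r is an assumption. Both halves are to be compared, so a reader would see the lower half too.

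Much of this stands, and it limits the weight of the point. It does not remove it. The lack of randomisation and the mismatch with the instruction follow from the text and hold for any r. Silence in the Updated SAP is not withdrawal, since it still collects both measures weekly. Seeing both halves is only a partial safeguard: in the same simulation at r = 0.1, when the upper half was falsely significant, the lower half lay below the waitlist in only 37% of runs (66 per arm) or 53% (200 per arm).

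Three stronger readings are tempting, and the documents do not support them:

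- **That a false benefit is to be expected.** A reader might infer a positive r from the line in MR Content that "Dyads will be informed that greater use may result in greater benefit to reinforce practice". That line points to expectancy within the MR arm, which is a different mechanism from the one modelled above. It could raise reports among heavy users without pushing light users below the waitlist. Nor is the sign of r known: if Veterans in more pain practise more, r is negative.
- **That the primary result is compromised.** The split does not alter the H1.1 analysis. Expectancy or self-report effects in the MR arm could enter the intention-to-treat contrast as well, but that is a separate matter which the split neither causes nor cures.
- **That the upper-half result will be a main claim.** The protocol says only that the weekly data allow dose-response work. Nothing gives this contrast prominence.

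**Conclusion.** The point holds as one of design and labelling. The rule as written gives contrasts that randomisation does not protect, contradicts the statement that all analyses follow intention to treat, and describes as recommended use something that a median, and still more a satisfaction score, does not measure.

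The size of any bias cannot be known from the documents. The 0.80r SD shift and the table rest on an assumed r, normal variables, no MR effect and a purely prognostic link. They show that modest correlations could matter, not that they exist. The harm is confined to an exploratory analysis. Confidence is high on the design and the label, and low on the size and direction of bias.

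**What to change.** 1. State in the Updated SAP whether the median split is kept.
2. Do not compare satisfaction halves with the waitlist as a per-protocol analysis. Report satisfaction descriptively within the MR arm.
3. Score adherence from the weekly 11-item reports against the MR Content instruction and report it descriptively. The frequency for other methods is given as a range, so fix in advance how it is counted.
4. Remove the per-protocol and recommended-use description from the median split.
5. If a use-based contrast with the waitlist is kept, label it exploratory and non-randomised, adjust it for the baseline value of the outcome, and except it from the intention-to-treat statement in Data Analysis.

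The cost is a little more text and one scoring rule for weekly reports that are already planned. The primary analysis does not change.

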Sample Size Power Analysis: Aim 1&2, H1.1-H1.2 & H2.1 estimates of statistical power are based on Aim 1 and initially the primary outcome of pain. Whereas dyad is the unit of randomization, we assess power based on separate analyses for Veterans and partners (one approach used). There are 4 major intervals of assessment (baseline, 1, 2, and 4-months). At the beginning of this study, we estimated attrition based off of a previous MR trial that had less than 5% attrition. Based on early recruitment at the primary site, we have adjusted recruitment goals to allow for approximately 33% attrition, and uneven recruitment across the three study sites. Assuming within-subject (outcome measurement) correlation of 0.5, the proposed sample size will provide 80% power (2-sided type I error rate of 0.05) to detect a “small-to-medium” effect size of 0.38 (Cohen’s d). For analyses stratified by site (in addition to evaluation by random effect assessment), the study will provide 80% power to detect a “medium-to-large” effect size of 0.66. By way of comparison, the pilot data presented above describes large effect sizes ($d = 0.81$ for pain symptom reduction). While this effect size was based on a relatively small sample of comparable patients ($n < 15$) and within-subject assessment (paired t -test), it provides good assurance that the proposed sample size is sufficient to detect realistic, medium size effects should they exist with the MR program. For secondary outcomes, we will use a type I error rate of 0.01 for multiple comparisons. For the sample and our described assumptions, this will provide 80% power to detect a “medium” effect size of 0.45.⁵⁹

Sample Size: Qualitative- Aim 3 sample size relies on the quality and richness of information obtained.⁶⁰ Conceptual saturation is the goal of qualitative research, and depends on data to support interpretations. Saturation has been noted to occur within the first 12 interviews.^{60,61} Our team has extensive experience in evaluating electronic technologies, and have found recruiting high and low volume users provides the richest dataset. To ensure representative data, we will conduct telephone interviews with a purposive (e.g., high or low MR utilization group) sub-sample of up to 84 individuals to achieve representation at each site (approximately 28 individuals/site).

Data Collection Procedures. Data will be collected using (1) self-report surveys; and (2) telephone interviews.

(1) Self-reported Survey Data.

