Interviewers will solicit respondents' attitudes, opinions, and reports about their preferences and the pros and cons of MR and/or participating in the practice groups, including their perceptions of usefulness. We will use standard communication techniques to stimulate discussion, with prompts (e.g., "tell me more"), summarizing statements, and silence. We have used these methods in several previous studies to gather data effectively. Additionally, in an effort to understand the factors that contribute to study attrition, a maximum of ten individuals who did not complete study activities may be contacted for a brief 15-minute voluntary telephone interview. These interviews will solicit respondents' experiences with the study and any difficulties that they experienced. Only participants who were lost to follow up and who had been assigned to the treatment arm will be contacted for these attrition interviews. Participants who officially withdrew from the study will be excluded from the pool of prospective interviews.

A total of 84 interviews (n=84 individuals), including participants lost to follow up and participants who have successfully completed the study, will be performed. We will attempt to interview both members of dyads to obtain conceptual saturation.

Data Analysis: The *intention to treat* principle will be used for all analyses irrespective of the extent of protocol compliance or dropout.⁹⁰ Whereas randomization is anticipated to balance both study arms on presenting demographic and clinical characteristics, including

within sites and by concomitant receipt of first line pain and/or PTSD treatment, continuous variables will be compared by student t-tests or Wilcoxon tests (depending on distributional properties); categorical variables will be compared by chi-square analyses.

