Missing data. Missing data will be tabulated by treatment arms and by assessment waves; comparison tests between arms will be conducted to assess potential attrition bias and to examine the missing data mechanism (e.g. missing at random). If missing rate is less than 10%, analyses with list wise deletion (missing values dropped from the analysis) will be performed (due to minimal concern over bias). Participants who are lost to follow-up and missing on post randomization outcome assessments will be included in additional comparison analyses that utilize multiple imputations of missing data to minimize bias due to differences between those with complete and incomplete data.

Dissemination Plan. Dissemination efforts will be led by the PI along with the VA operational (e.g. OPCCCT and CCO), clinical stakeholders (e.g. mental health and pain clinicians), and the Tampa R&DS VEC. We will publish findings in peer-reviewed journals and present findings at national and international meetings including Medicine 2.0, the international conference for internet-based health research ([name]) and Association of Military Surgeons of the United States (AMSUS) Annual Continuing Education Meeting. Dissemination activities will inform VHA operational initiatives and clinical practice (Table 2). The deployment of Whole Health models of care nationally will provide a natural setting for dissemination. The Tampa VEC will support dissemination efforts to Veterans, their families, and to Veteran Service Organizations.

Table 2. Dissemination Plan

Format	Target Audience	Potential Use or Outcomes
1. Mission Reconnect for Veterans and their partners		
Briefing	Clinicians in Mental Health and Pain Clinics, VEC	
 • MR as an option for non-pharmacological self-care management for chronic pain
2. Linking study findings to operational and clinical initiatives		
Reports/Oral Presentation	Office of Mental Health	
 • Guidelines for using MR to support clinical care
	Connected Care Office	
 • Support operational mission and provide insight on usability and application of MR
	Office of Patient Centered Care & Cultural Transformation &	
 • Support operational mission and provide insight on usability and application of MR

Flagships		• Lessons learned and MR use strategies
3. Mission Reconnect in the VA for self-care management		

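### The listwise-deletion rule below 10% missingness conflicts with the intention-to-treat principle, and no main method is named for 10% or more, although about 33% attrition is planned

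*Combined protocol and SAP*

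**What the plan says.** - **Principle.** Protocol, Data Analysis: the intention-to-treat "principle will be used for all analyses irrespective of the extent of protocol compliance or dropout".
- **Deletion rule.** Protocol, Missing data: "If missing rate is less than 10%, analyses with list wise deletion (missing values dropped from the analysis) will be performed". The reason given is that bias is of little concern at that level.
- **Participants lost to follow-up.** Same section: those with missing outcomes after randomisation "will be included in additional comparison analyses that utilize multiple imputations of missing data to minimize bias". The section also plans between-arm tests of missingness, partly to examine the missing-data mechanism.
- **Expected attrition.** Protocol, Sample Size Power Analysis: the initial basis was "a previous MR trial that had less than 5% attrition", but now "we have adjusted recruitment goals to allow for approximately 33% attrition". The section on human subjects involvement repeats the 33% against 600 dyads.
- **Main model.** Protocol, Hypotheses Aims 1 & 2: a general linear mixed model with baseline as one of four time points, plus an ANCOVA for the baseline-to-month-1 effect. The updated SAP keeps the mixed model with continuous time. It says nothing about missing data or intention to treat, so the protocol's Missing data section is the only rule in force.

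**The concern.** Deleting incomplete cases does not fit a principle that covers every analysis whatever the dropout. Nor does handling participants lost to follow-up in analyses described as additional. The deletion also gains nothing, because a mixed model fitted by likelihood uses each available record and needs no deletion at any missing rate.

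Two gaps make this worse. The missing rate has no stated level, so the same data could trigger the rule or not. For 10% or more, which is the planned case at month 4, no main method is named. The choice could then be made after the data are seen.

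Deletion biases the comparison mainly when dropout works differently in the two arms. The documents report no such difference, but the design allows one:

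- Waitlist dyads get the program only after completing data collection, and the protocol expects the waitlist offer to help retention.
- The weekly utilization report has 11 items for treated participants and 4 for controls, and only treated participants get satisfaction items.
- Outcomes are self-reported by people who know their arm.

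Finally, comparing missingness between arms cannot establish that data are missing at random. Multiple imputation as usually run and the likelihood mixed model both rest on that assumption, and no planned analysis departs from it.

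**Working it through.** The Missing data section has no computed figure to reproduce. The relevant plan numbers are the 10% threshold, the 33% planned attrition and the three follow-ups (months 1, 2 and 4). The power figure in Sample Size Power Analysis does not bear on this point.

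**1. When would the rule apply?** 33% is more than three times 10%, so the rule would not apply to month-4 or overall missingness if attrition is as planned. On a per-wave reading, assume that 33% accrues at a constant rate over four months (an assumption, not in the documents). Missingness at month t is then 1 − 0.67^(t/4):

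- month 1: 1 − 0.67^0.25 = 9.5%
- month 2: 1 − 0.67^0.5 = 18.1%
- month 4: 33%

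Deletion would be triggered at month 1 only. The month-1 ANCOVA would in any case lose anyone without a month-1 score.

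**2. How many Veterans could be lost below the threshold?** Take 9% missing at each of three follow-ups (an assumed value just under the trigger) and person-level deletion:

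- the same people missing each time: 9%
- independent waves: 1 − 0.91³ = 24.6%, about 25%

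The range depends on reading the rate per wave. If the rate counted incomplete persons, 25% would exceed 10% and the rule would be off.

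**3. How much bias near the threshold?** This is an illustrative simulation with assumed settings:

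- 400,000 per arm, giving Monte Carlo error of roughly √(2/400,000) = 0.002
- correlations between visits of 0.4 to 0.6
- true month-4 effect −0.380 SD, matching the design effect of 0.38
- 9.9% missing at month 4, with dropout depending on month-1 pain (log odds per SD as shown; 0.7 is an odds ratio of e^0.7 = 2.0)

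| Slope, MR / control | Listwise ANCOVA | Listwise change score | Available-data likelihood |
|---|---|---|---|
| 0.7 / 0.7 | −0.383 | −0.383 | −0.383 |
| 0.7 / 0 | −0.395 | −0.373 | −0.381 |
| 0.7 / −0.7 | −0.416 | −0.369 | −0.381 |

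For listwise ANCOVA the bias is 0.395 − 0.380 = 0.015 and 0.416 − 0.380 = 0.036 SD in favour of MR, or 4% and 9% of 0.38. With the same dropout mechanism in both arms it agrees with the available-data estimate. The listwise change score errs the other way, by 0.007 and 0.011 SD, so the direction depends on the estimator. The available-data estimate stays within simulation error of the truth throughout.

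**The case against.** The strongest reply is that the plan already names a mixed model with baseline among its time points. Fitted by likelihood, it keeps anyone with a recorded assessment. Group assignment is given once baseline collection is complete, so every randomised Veteran should have one. The parenthesis in the deletion rule speaks of missing values, which can mean records rather than persons. The additional imputation analyses can be read as sensitivity analyses beside that model. On this reading little is lost, and the conflict is partly one of wording. That reading is available, but the documents never state it. An analyst who ran complete cases below 10% would be following the text.

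It is also fair that the simulated bias is small, that its settings are assumptions, and that ANCOVA at month 4 stands in for an analysis which the protocol reserves for month 1. The change-score column may be closer to the planned model. The size should therefore be read as modest and uncertain in direction.

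A reader might infer that a third of the sample, 0.33 × 600 = 198 dyads, falls outside the main analysis. The documents do not support this. The rule is off at that level of missingness, and no section removes dropouts from the mixed model. Nor do they support quoting the bias of a completer analysis at 33% attrition. That analysis is not prescribed, and such a bias also requires dropout to depend on pain differently by arm, which no section reports.

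**Conclusion.** The point holds as a conflict and a gap in the text. The deletion rule, and the placing of participants lost to follow-up in additional analyses, do not match the intention-to-treat statement, and the updated SAP does not resolve this. The missing rate is undefined, and the main method at 10% or more is unstated.

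Below the threshold, the rule could discard 9% to 25% of Veterans, given person-level deletion and a per-wave rate of 9%. In the assumed scenarios the resulting listwise ANCOVA bias is about 0.015 to 0.036 SD if dropout differs by arm, and nil if it works alike in both. At the planned 33%, the weakness is that no primary method is fixed in advance. It has not been shown that a third of the data would be deleted.

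**What to change.** Reconcile the protocol's Data Analysis, Hypotheses Aims 1 & 2 and Missing data sections with the updated SAP:

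1. Delete the 10% listwise rule. The missing rate then needs no definition as a trigger.
2. State that the primary analysis is the likelihood-based mixed model on all randomised Veterans, using every available assessment with baseline in the outcome vector, whatever the missing rate.
3. Keep multiple imputation as a sensitivity analysis, with the weekly single-item pain scores in the imputation model.
4. Add a delta-adjusted or reference-based sensitivity analysis for data not missing at random. Keep the between-arm tabulation of missingness as description only.

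The cost is SAP wording and one or two extra sensitivity runs. No new data are needed.
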